mRS	Modified Rankin scale
MT	Mechanical thrombectomy
NCCT	Non-contrast computed tomography
NIHSS	National Institute of Health stroke scale
PPS	Per-protocol set
PT	Preferred term
SAE	Serious adverse event
SAP	Statistical analysis plan
SAS	Statistical analysis system
SD	Standard deviation
sICH	Symptomatic intracerebral hemorrhage
SOC	System organ class

1 STUDY OVERVIEW

This Statistical Analysis Plan (SAP) is developed based on the most recent study protocol (Version 3.0, 20-Aug-2019) and Case Report Form (CRF, Version 1.4, 13-Nov-2018), and details the statistical analysis strategies and methods for the study.

This SAP predefines the statistical analysis population, variables and analysis methods before database lock to ensure the reliability of the study results.

1.1 STUDY DESIGN AND RANDOMIZATION

This is a multicenter prospective randomized clinical trial with open-label treatment and blinded outcome assessment (PROBE). The study will run for 4 years in intervention centers. Randomization will be stratified by center. The treatment allocation is 1:1 for:

- Direct IAT (MT),
- IVT followed by IAT (IVT plus MT)

[figure not shown]

Figure 1 Patient flow in the trial

The intervention group will undergo immediate intra-arterial treatment (IAT) using a stent retriever, as recommended by the steering committee. Patients in the control group will receive alteplase intravenous treatment (IVT) (0.9 mg/kg with a maximum dose of 90 mg), followed by IAT using a stent retriever.

Local application (intra-arterial) of alteplase is allowed in any of the patients included in the DIRECT-MT if necessary. Patients pre-treated with IVT should not receive more than 30mg alteplase during intra-arterial treatment. Delivery of alteplase in shots of 5 mg in 5-10 minutes intervals is recommended. An equivalent dose of 400,000 U urokinase, delivered in shots of 50.000 - 100.000 U, in 5-10 minutes time intervals, is also accepted as escape medication in individual cases. If successful reperfusion (eTICI 2b-3) is not achieved in the direct MT group, IVT with 0.9 mg/kg may be initiated if the 4.5 hour window or maximum dose is not exceeded.

1.2 STUDY OBJECTIVES

The primary objective of this trial is to assess the effect of direct IAT compared with IVT followed by IAT, on functional outcome in patients with acute ischemic stroke (AIS), caused by an anterior circulation occlusion that is confirmed by Computed tomography angiography (CTA).

The secondary objective is to explore for superiority of direct IAT relative to IVT followed by IAT.

The tertiary objective is to assess the effect of direct IAT compared with IVT with IAT on neurological recovery (NIHSS), infarct size and occurrence of Symptomatic intracerebral hemorrhage (sICH).

The fourth objective is to collect thrombi and to analyze them with respect to their potential for treatment effect modification.

1.3 STUDY OUTCOMES

Primary outcome:

The primary outcome is the score on the modified Rankin Scale (mRS) ([Table 1 in Appendix](#)) at 90 days (± 14 days). The mRS is the preferred disability parameter for clinical trials in stroke. The mRS is an ordinal hierarchical scale incorporating six categories from 0 up to and including 5, and describes the range of disability encountered post stroke. "Death" is assigned a score of 6. Assessment of outcome on the mRS will be performed by outcome committee, blinded to the allocated and actually received treatment. Their assessment will be based on standardized reports of a telephone interview by trained research personnel who are not aware of treatment allocation.

Secondary outcomes:

- Death within 90 days (± 14 days)

- Pre-interventional recanalization
- extended treatment in cerebral ischemia scale (eTICI) score on final angiography of IAT ([Table 2 in Appendix](#))
- Recanalization rate at 24-72 hours, assessed with CTA
- Score on the NIHSS at 24±6 hours and 5 -7 days. ([Table 3 in Appendix](#))
- Final infarct volume at 5-7 days. Final infarct volume will be assessed with the use of an automated, validated algorithm. Infarct size at day 5-7 will be compared with plain computed tomography (CT) and perfusion CT results (if available) at baseline.
- Dichotomized mRS of 0-1 vs. 2-6 at 90 days (±14 days)
- Dichotomized mRS of 0-2 vs. 3-6 at 90 days (±14 days)
- Dichotomized mRS of 0-3 vs. 4-6 at 90 days (±14 days)
- Score on the EuroQol-5 dimensions-5 level (EQ5D-5L) ([Table 4 in Appendix](#)) and Barthel index (BI) ([Table 5 in Appendix](#)) at 90 days (±14 days)

Safety outcomes:

- Hemorrhages according to the Heidelberg criteria [1]
- sICH scored according to the Heidelberg criteria [2]
- Embolization in new territory on angiography during IAT
- Occurrence of aneurysma spurium
- Occurrence of groin hematoma
- Infarction in new territory at 5-7 days ([Table 6 in Appendix](#))
- Death from all causes within 90 days (±14 days)

1.4 SAMPLE SIZE CALCULATION

We based our estimations on the distribution of the mRS in the control group of the trial, which we derived from the intervention group of the MR CLEAN trial [3]: mRS 0: 3%; mRS 1: 9%; mRS 2: 21%; mRS 3: 18%; mRS 4: 22%; mRS 5: 6% and mRS 6: 21%. We assumed a favorable treatment effect with a common odds ratio (cOR) of 1.163, corresponding to a 4% absolute increase in the rate of mRS scores of 0-2. The main purpose is to demonstrate non-inferiority, that is, the lower limit of the two-side 95% confidence interval does not cross the pre-specified cOR non-inferiority Cutoff of 0.8. In a simulation with 5000 runs we computed the proportion of positive trials, for a given sample size. A sample size of 710 was determined to detect the pre-defined non-

inferiority with a power of 80% and two-sided alpha of 0.05. Using covariate adjustment with at most 25%, a conservative 15% sample size reduction can be achieved, plus 5% dropout rate, leading to a final sample size of 636, 318 per arm.

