2.3.2.1 Primary efficacy outcome

The primary effect parameter is the common odds ratio, which will be estimated by ordinal logistic regression (proportional odds model), which represent the shift on the full distribution of the modified Rankin Scale at 90±14 days. Estimations will be adjusted by known prognostic variables such as age (median), pre-stroke mRS (continuous), time from symptom onset to randomization (" \leq Q1", ">Q1, \leq Q2", ">Q2, \leq Q3", ">Q3"), stroke severity (NIHSS, median) and collaterals (Grade 0-1, Grade 2-3). Adjusted and unadjusted estimations and their corresponding 95% confidence intervals will be reported. To assess non-inferiority of direct MT compared to IVT with MT, we will assess whether the 95% CI lower bound of the adjusted common odds ratio cross our pre-specified non-inferiority boundary (0.8).

The following SAS procedure will be used for ordered logistic regression analysis (proportional odds model):

```
Proc logistic data=XXX;  
Class TRT FactorA ...;  
Model mRS90= TRT AGE FactorA ...;
```

Run;

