3 CHANGES TO PLANNED ANALYSES FROM THE PROTOCOL

Protocol version (Date)	Major Changes to Planned Analyses from the Protocol
Version 2.0 (31-Aug-2018)	
 ● Recalculated the sample size according to the modified good outcome (Section 4.5 of the protocol) 
After revision:
 
We assumed a favorable treatment effect with a common odds ratio (cOR) of 1.163, corresponding to a 4% absolute increase in the rate of mRS scores of 0-2. The main aim of the trial is to demonstrate non-inferiority. To do so, the lower limit of the two-sided 95% confidence interval of the cOR should not cross the pre-specified non-inferiority boundary of 0.8.
 
In a Monte Carlo simulation with 5000 runs we computed the proportion of positive trials, for a given sample size. A sample size of 710 was determined to detect the pre-defined non-inferiority with a power of 80% and two-sided alpha of 0.05. Using covariate adjustment with at most 25%, a conservative 15% sample size reduction can be achieved, plus 5% dropout rate, leading to a final sample size of 636, 318 per arm.
 
Before revision:
 
We based our estimations on the distribution of the modified Rankin Scale (mRS) in the control group of the trial, which we derived from the intervention group of the MR CLEAN trial (9): mRS 0: 3%; mRS 1: 9%; mRS 2: 21%; mRS 3: 18%; mRS 4: 22%; mRS 5: 6% and mRS 6: 21%. We assumed a favorable treatment effect with a common odds ratio (cOR) of 1.54, which corresponds to an absolute risk difference of having a score on the modified Rankin Scale of 0-2 of approximately 8%. The main purpose is to demonstrate non-inferiority, that is, the lower limit of the 95% confidence interval does not cross the pre-specified cOR non-inferiority Cutoff of 0.8. In a simulation with 5000 runs we computed the proportion of positive trials, for a given sample size. This yielded a sample size of 680, providing 99% power to detect a true treatment effect, with two-sided alpha =0.05. In the analysis we will use covariate adjustment, which reduces the required sample size with 25% (28, 29).

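### The 15% sample-size cut for covariate adjustment does not keep 80% power when the adjusted common odds ratio is tested against a fixed 0.8; power at 604 evaluable is about 73–78%, and the stated 4% gain is 3.4%

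*SAP*

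**What the plan says.** Section 1.4 takes the control-group mRS distribution as "mRS 0: 3%; mRS 1: 9%; mRS 2: 21%; mRS 3: 18%; mRS 4: 22%; mRS 5: 6% and mRS 6: 21" per cent. It sets the effect as follows: "We assumed a favorable treatment effect with a common odds ratio (cOR) of 1.163", and describes this as "corresponding to a 4% absolute increase in the rate of mRS scores of 0-2". Non-inferiority is shown if the lower limit of the two-sided 95% interval "does not cross the pre-specified cOR non-inferiority Cutoff of 0.8". Simulation gave 710 patients for 80% power. The section then says "Using covariate adjustment with at most 25%, a conservative 15% sample size reduction can be achieved", adds 5% for dropout and arrives at 636, or 318 per arm.

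Section 2.3.2.1 fixes the analysis: "Estimations will be adjusted by known prognostic variables such as age (median), pre-stroke mRS (continuous), time from symptom onset to randomization", together with NIHSS and collaterals. For the decision, "we will assess whether the 95% CI lower bound of the adjusted common odds ratio cross our pre-specified non-inferiority boundary (0.8").

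Section 3 lists the calculation among the changes made with protocol version 2.0: "Recalculated the sample size according to the modified good outcome (Section 4.5 of the protocol"). Section 1.4 does not say whether 1.163 and 0.8 were set as adjusted or unadjusted cORs. It does not report a simulation of the adjusted test.

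**The concern.** A percentage saving from covariate adjustment is normally worked out for a test against an odds ratio of 1. There, the whole distance to be detected grows when the model is adjusted, because the adjusted log odds ratio lies further from zero than the unadjusted one. Here the test is against 0.8. The distance is ln(1.163) − ln(0.8), and its larger part is the margin, which stays where it is. The same percentage cannot simply be carried over.

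At stake is the stated power. If the cut is not earned, the trial is somewhat more likely to miss non-inferiority than the plan says. A second point is that the 4% describes a larger assumed benefit than the cOR that produced 710.

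**Working it through.** **Inputs.** From section 1.4: the mRS distribution (0–2 sums to 3 + 9 + 21 = 33%), cOR 1.163, margin 0.8, two-sided alpha 0.05, power 80%, N = 710, cut 15% (maximum 25%), dropout 5%. From section 1.1: allocation 1:1. From section 2.3.2.1: the covariates, their coding, and the test of the adjusted cOR against 0.8.

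**1. Reproduce the plan's figures.** The Whitehead formula for ordinal data is

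N = 12 (z₀.₉₇₅ + z₀.₈₀)² / {[ln(1.163) − ln(0.8)]² (1 − Σp̄³)}.

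- ln(1.163) = 0.151 and ln(0.8) = −0.223, so the distance is 0.374.
- The mean of the two arms' mRS distributions gives 1 − Σp̄³ = 0.9647.
- N = 12 × 2.8016² / (0.3741² × 0.9647) = 697.
- Power at 710 is 80.7% by formula and 80.4% in 5000 simulated trials. The 710 reproduces, with no covariates in the calculation.
- 710 × 0.85 = 603.5, taken as 604. Then 710 × 0.85 / 0.95 = 635.3, taken as 636. The arithmetic chain is right.
- Without covariates, the standard error at 604 is √[12 / (604 × 0.9647)] = 0.1435, and power is Φ(0.374/0.1435 − 1.96) = 74.1%.

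**2. What adjustment does.** The covariates were coded as in section 2.3.2.1: age and NIHSS split at the median, time in quartiles, collaterals in two grades, pre-stroke mRS linear. The SAP gives no covariate effects. Their relative sizes, the share with good collaterals (60%) and the pre-stroke mRS mix (0/1/2 at 80/15/5%) are assumptions. Overall strength was scaled so that a test against 1 would need 15% or 25% fewer patients.

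| | 15% covariates | 25% covariates |
|---|---|---|
| SE ratio, adjusted to unadjusted | 1.007 | 1.013 |
| Unadjusted 1.163 becomes, adjusted | 1.179 | 1.193 |

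As a check on the scaling, 1 − [1.007 × ln(1.163)/ln(1.179)]² = 14.7%, and the same formula with 1.013 and 1.193 gives 24.9%. These match the intended 15% and 25% within rounding.

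**3. Power at 604 against a fixed 0.8.** Power = Φ{[ln(adjusted cOR) − ln(0.8)] / SE − 1.96}, with SE = 0.1435 × ratio.

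- 1.163 unadjusted, 15%: (0.1646 + 0.2231)/0.1445 = 2.684, so 76.5%.
- 1.163 unadjusted, 25%: (0.1765 + 0.2231)/0.1454 = 2.749, so 78.5%.
- 1.163 adjusted, 15%: 0.3741/0.1445 = 2.589, so 73.5%.
- 1.163 adjusted, 25%: 0.3741/0.1454 = 2.574, so 73.0%.

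Simulations of 5000 trials each (standard error 0.6 points) gave 76.1%, 78.2%, 73.4% and 72.6%. A separate model with a single normal prognostic score gave 76.5%, 78.4%, 73.5% and 72.9%. Once overall strength is fixed, the covariate structure matters little.

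**4. What 80% would take.**

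- If 1.163 is unadjusted, about 658 evaluable patients are needed (15% covariates) or 628 (25%). Against 710 that saves 7% or 12%.
- If 1.163 is adjusted, about 708 to 717 are needed, so nothing is saved.
- On the unadjusted reading, 80% at 604 needs covariates worth about 32%, above the plan's own maximum of 25%.
- The full 15% is kept only if 0.8 is also an unadjusted value and is converted for the adjusted test. With 15% covariates it becomes about 0.78 (0.7835), and power is then 80.7%. Section 2.3.2.1 makes no such conversion.

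**5. The 4%.** Control odds of mRS 0–2 are 0.33/0.67 = 0.4925. Multiplied by 1.163 they are 0.5728, a proportion of 0.5728/1.5728 = 36.4%, which is a gain of 3.4 points. A gain of 4 points needs (0.37/0.63)/(0.33/0.67) = 1.192.

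**The case against.** The best case against this has four parts.

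First, the shortfall is small. Section 1.4 applies 1.163 to a raw mRS distribution, so the unadjusted reading fits best. On that reading power is 76–78%, only 2 to 4 points short. This stands as a statement of size. At the 15% the plan actually uses, though, both readings fall more than 3 points short.

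Second, if the intended effect was the 4-point gain, power recovers. At cOR 1.192, power at 604 is about 79% with no covariate gain and, on the unadjusted reading, about 82–84% with 15–25% covariates. But cOR 1.192 would need only about 614 patients before any cut. The stated 710 shows that 1.163 was the effect used and that 4% is the figure out of line.

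Third, the covariate effects are assumed. This is true and limits the precision of any single power value. It does not rescue the 15%, because two different covariate structures give nearly the same answers across the plan's own range.

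Fourth, 604 allows for 5% loss. If all 636 had an outcome, the unadjusted reading would give about 78.6% and 80.5% with 15% and 25% covariates. But 604 is the plan's own planning number, and the dropout allowance is there to be spent.

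It is also fair to say that section 2.3.2.1 does apply 0.8 on the adjusted scale. What is not stated is the scale on which 0.8 was chosen.

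**Conclusion.** The concern holds. The chain from 710 to 636 is arithmetically correct, but the claim that it preserves 80% power does not follow for the test the SAP specifies. At 604 evaluable, power is about 76–78% if 1.163 is an unadjusted cOR and about 73% if it is adjusted, a shortfall of roughly 2 to 7 points. These figures rest on a proportional odds model, covariates worth 15–25% in a superiority test, and assumed relative covariate effects.

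The 4% is wrong on the plan's own inputs and needs no assumption to show it: the gain is 3.4 points.

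Neither point affects the validity of the non-inferiority decision rule. What changes is how likely the trial is to succeed if 1.163 is true, and how the assumed benefit is described.

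**What to change.** Keep N = 636 and amend section 1.4:

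1. State whether 1.163 and 0.8 are adjusted or unadjusted cORs.
2. Re-run the simulation with the adjusted model of section 2.3.2.1 against 0.8 at 604 evaluable, give the covariate effects assumed, and report whatever power results.
3. Remove the statement that a 15% reduction keeps 80% power and put the simulated figure in its place.
4. Replace the 4% absolute increase with 3.4% (33.0% to 36.4%), since 1.163 is the effect that produces 710.

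Section 3 traces this text to section 4.5 of the protocol, so the correction should be recorded there.

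The cost is some SAP wording and one simulation run. The stated power will probably be a little less favourable. Sample size, model, margin and analysis set do not change.

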1.5 STUDY PROCEDURES

Before starting the study, patients or their guardians must read and sign the informed consent approved by the current Ethics Committee (EC). All research steps should be carried out within the time window specified in the study protocol.

All patients will undergo assessment of the NIHSS at baseline, 24±6 hours and 5-7 days, which is routine in clinical procedure. It will be carried out by certified assessors. Patients will undergo NCCT and CTA at baseline. After 24-72 hours, CTA is repeated to determine recanalization. At 5-7 days, patients will undergo non-contrast computed tomography (NCCT) to assess infarct size.

In addition, this trial also makes use of "waste material": retrieved thrombi during intervention. These thrombi will be stored in the participating study centers for follow-up analysis.

1.5.1 Procedures

All the procedures to be recorded are listed in [Table 1](#).

Table 1 Procedures

Items	Procedures(includes but not limited to:)
Demography	Date of birth (based on valid identity documents), sex, age
Medical History	Disease history, smoking/alcohol drinking history, medications
Modified Rankin Scale	Disability level, ranging from 0~5
Glasgow coma Scale	Eye Opening, Best Verbal Response, Best Motor Response
Vital Signs	Systolic/diastolic blood pressure, heart rate, body temperature, height, weight
NIHSS	Level of consciousness (LOC), LOC Questions, LOC Commands, Best Gaze, Visual, Facial palsy, Motor arm, Motor leg, Limb ataxia, Sensory, Best language, Dysarthria, Extinction and Inattention
Laboratory tests	Serum glucose, Activated Partial Thromboplastin Time (APTT), International normalized ratio (INR), Thrombocyte count, Serum creatinine
eTICI	eTICI classification includes 0, 1, 2a, 2b, 2C and 3
EQ5D-5L score	Mobility, Self-Care, Usual-Activities, Pain/Discomfort, Anxiety/Depression
BARTHEL index	Feeding, Bathing, Grooming, dressing, Bowels, Bladder, Toilet use, Transfers(bed to chair and back), Mobility(on level surfaces), Stairs
Neuroimaging	CT, CTA, MRI and other imaging examinations

2 STATISTICAL METHODOLOGY

2.1 STATISTICAL VARIABLES

2.1.1 Background and demographic characteristics

The demographic and baseline information will include age, sex, medical history, smoking history and medications used at home.

2.1.2 Efficacy

2.1.2.1 Primary efficacy variables

Primary efficacy outcome is mRS score change at 90 days (± 14 days), which will be blindly evaluated by an independent Outcome Assessment Committee.

The mRS is the preferred disability parameter for clinical trials in stroke. The mRS is an ordinal hierarchical scale incorporating six categories from 0 up to and including 5, and describes the range of disability encountered post stroke. "Death" is assigned a score of 6 ([Table 1 in Appendix](#)).

2.1.2.2 Secondary efficacy variables

- Death within 90 days (± 14 days)
- Pre-interventional recanalization
- eTICI score on final angiography of IAT. ([Table 2 in Appendix](#))
- Recanalization rate at 24-72 hours, assessed with CTA
- Score on the NIHSS at 24 \pm 6 hours and 5 -7 days. ([Table 3 in Appendix](#))
- Final infarct volume at 5-7 days. Final infarct volume will be assessed with the use of an automated, validated algorithm. Infarct size at day 5-7 will be compared with plain CT and perfusion CT results (if available) at baseline.
- Dichotomized mRS of 0-1 vs. 2-6 at 90 days (± 14 days)
- Dichotomized mRS of 0-2 vs. 3-6 at 90 days (± 14 days)
- Dichotomized mRS of 0-3 vs. 4-6 at 90 days (± 14 days)
- Dichotomized mRS of 0-4 vs. 5-6 at 90 days (± 14 days)
- Dichotomized mRS of 0-5 vs. 6 at 90 days (± 14 days)

- Score on the EQ5D-5L and Barthel index at 90 days (± 14 days)

Pre-interventional recanalization: Recanalization rate (eTICI 2b, 2c or 3) before patients received mechanical intra-arterial treatment according to the DSA.

Recanalization rate at 24-72 hours: defined as the proportion of patients in whom recanalization as determined on 24-72 hours CTA is achieved.

eTICI score: eTICI assessment will be performed post IAT. The eTICI classification includes 0, 1, 2a, 2b, 2c and 3 ([Table 2 in Appendix](#)).

NIHSS score: The NIHSS is an ordinal hierarchical scale to evaluate the severity of stroke by assessing a patient's performance. Scores range from 0 to 42, with higher scores indicating a more severe deficit ([Table 3 in Appendix](#)). NIHSS assessment will be performed at baseline, 24 ± 6 hours post operation and 5-7 days post operation.

The EuroQoL 5-dimensions 5-level (EQ-5D-5L) questionnaire is a standardized measure of health outcome that has been used extensively in patients with stroke ([Table 5 in Appendix](#)). EQ5D-5L assessment will be performed at 90 ± 14 days post operation.

The Barthel index (BI) is an ordinal scale used to measure performance in 10 activities of daily living (ADL). Test scores range from 0 to 100, with higher scores indicating better performance in these daily activities ([Table 4 in Appendix](#)). BI assessment will be performed at 90 ± 14 days post operation.

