2.1.3.4 Neuroimaging

CT and CTA will be performed at baseline and follow-up visit and the findings of which will be blindly evaluated by an independent Imaging Committee (Core lab), including hyperdense, the Alberta Stroke Program Early CT Score (ASPECTS), another occlusion location of anterior circulation except target lesion, anterior communicating artery (AComA), intracranial hemorrhages ([Table 7 in Appendix](#)), midline shift present, target vessel stent placement, modified arterial occlusive lesion classification (mAOL, ([Table 8 in Appendix](#))), vascular occlusion, etc.

The newly affected territory of the middle cerebral artery was graded by the systematic quantitative scoring system, e.g. ASPECTS. It will be performed at baseline visit and follow-up visit. ASPECTS is allotted 10 points, including caudate, lentiform, internal capsule, insular cortex, M1, M2, M3, M4, M5, M6. One point is subtracted for an area of early ischaemic change, such as focal swelling, or parenchymal hypoattenuation, for each of the defined regions. A score of 0 indicates diffuse ischaemia throughout the territory of the middle cerebral artery.

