2.3.2.2 Secondary efficacy outcome

Continuous secondary efficacy outcomes are mainly infarct size at 5-7 days after operation and recanalization rate before intervention as well. Analysis for these outcomes will be mainly based on statistical descriptions. Where necessary, analysis of variance or corresponding non-parametric test will be used for between-group comparisons. If applicable, the linear regression analysis will be used with adjustment for the same covariate variables as the primary outcome analysis. When deemed necessary, log or other common transformation of non-normal distribution will be used.

Categorical secondary outcomes include mortality at 90 days after operation, recanalization rate at 24-72 hours, dichotomized mRS score at 90 days after operation (0-1 vs. 2-6, 0-2 vs. 3-6, 0-3 vs. 4-6), successful recanalization before and after Mechanical thrombectomy (MT), and eTICI score at MT final angiography. Chi-square test will be used for comparison between the two groups, or Fisher's exact test will be used for comparison when applicable. The categorical secondary outcomes will be analyzed by logistic or ordered regression analysis to provide a common odds ratio and its confidence interval, if applicable. The adjustment method is the same as that in the primary outcome analysis.

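### The SAP does not define the baseline CT comparison for day 5-7 infarct size, and its infarct-volume model does not name baseline ASPECTS, which is already being read

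*SAP*

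**What the plan says.** Infarct size is part of the tertiary objective (SAP 1.2), and final infarct volume at 5-7 days is a listed secondary outcome (SAP 1.3 and 2.1.2.2).

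- **Measurement.** SAP 2.1.2.2: "Final infarct volume will be assessed with the use of an automated, validated algorithm". SAP 1.5 assigns the scan: at 5-7 days "patients will undergo non-contrast computed tomography (NCCT) to assess infarct size".
- **Baseline comparison.** SAP 2.1.2.2: "Infarct size at day 5-7 will be compared with plain CT and perfusion CT results (if available) at baseline". Section 1.3 says the same.
- **Baseline scans.** SAP 1.5: "Patients will undergo NCCT and CTA at baseline". Perfusion CT is not among them.
- **Analysis.** SAP 2.3.2.2 treats infarct size mainly descriptively, with analysis of variance or a non-parametric test where needed, and allows a log or other transformation. It adds: "If applicable, the linear regression analysis will be used with adjustment for the same covariate variables as the primary outcome analysis".
- **Covariates.** SAP 2.3.2.1: "Estimations will be adjusted by known prognostic variables such as age (median), pre-stroke mRS (continuous), time from symptom onset to randomization". The list goes on to baseline NIHSS and collateral grade.
- **ASPECTS.** SAP 2.1.3.4 includes it in the blinded core-lab reading of CT and says: "It will be performed at baseline visit and follow-up visit". Section 2.3.4.4 plans summary statistics for ASPECTS and its change from baseline, plus a frequency table by arm. That section falls under the safety analysis, which section 2.3.4 places on the per-protocol set.

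**The concern.** There are two linked gaps.

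First, the outcome definition promises a comparison with baseline imaging, but the methods section does not carry it out. The automated algorithm is stated for the final volume only. No baseline quantity is named for plain CT or for perfusion CT, and no statistic links baseline to day 5-7. An analyst could settle, with the data in view, which baseline reading to use, in which patients and in what form.

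Second, none of the named covariates for the volume regression is a direct reading of how much tissue already looked ischaemic on the baseline scan. ASPECTS is such a reading. It is already planned at baseline by a blinded core lab, yet the plan gives it no stated role in the volume analysis.

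What is at stake is modest: a clear definition for one secondary outcome, and some precision in its between-arm estimate.

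**Working it through.** **Step 1. Trace the baseline comparison through the SAP.**

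- Sections 1.3 and 2.1.2.2 announce it and name two sources: plain CT and, where it exists, perfusion CT.
- Section 1.5 schedules plain CT for every patient at baseline, but not perfusion CT.
- Section 2.3.2.2 lists descriptive statistics, analysis of variance or a non-parametric test, and a covariate-adjusted linear regression. All of these compare the arms. None compares day 5-7 with baseline.
- Sections 2.3.4.4 and 2.1.3.4 deal with ASPECTS but do not connect it to infarct volume.

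The comparison is therefore announced without a named quantity or method.

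**Step 2. Check the covariates.** Those carried from section 2.3.2.1 are age, pre-stroke mRS, time from onset to randomization, NIHSS and collaterals. Baseline ASPECTS is not named.

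**Step 3. Size of the gain from adding ASPECTS.** The SAP states no variance, effect size or power for infarct volume, so it has no figure of its own to reproduce. The one input needed is the partial correlation r between baseline ASPECTS and final volume (transformed if needed), given the other covariates. The SAP does not give it; a range of 0.2 to 0.5 is assumed.

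In a linear model for a randomized comparison, adding the covariate multiplies the residual variance by 1 − r². Hence:

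- reduction in standard error = 1 − √(1 − r²)
- equivalent increase in sample size = 1/(1 − r²) − 1

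| r (assumed) | 1 − r² | Fall in standard error | Equivalent extra patients |
|---|---|---|---|
| 0.2 | 0.96 | 2.0% | 4.2% |
| 0.3 | 0.91 | 4.6% | 9.9% |
| 0.4 | 0.84 | 8.3% | 19.0% |
| 0.5 | 0.75 | 13.4% | 33.3% |

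**Step 4. The same gain as a detectable difference.** Section 1.4 gives 318 per arm (710 × 0.85 = 603.5; 603.5 / 0.95 = 635.3, rounded up to 636). Borrowing the 80% power and two-sided 0.05 that section 1.4 sets for the primary outcome, the detectable difference without ASPECTS is (1.960 + 0.842) × √(2/318) = 0.222 residual SD. Multiplying by √(1 − r²) gives 0.218 at r = 0.2 and 0.192 at r = 0.5.

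**Step 5. Reach of a perfusion CT comparison.** The SAP does not say how many patients will have baseline perfusion CT. If the share were 20% to 80% (assumed), the comparison would cover about 636 × 0.2 = 127 to 636 × 0.8 = 509 patients.

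**The case against.** A fair defence has several parts, and much of it stands.

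- **The SAP does not plan infarct growth.** A reader might infer that a volume change is to be calculated and that the baseline scans cannot supply it. The document does not support this. It says only that infarct size will be compared with baseline results; no change variable appears, and nothing says that plain CT cannot yield a volume.
- **The comparison may be possible in every patient.** A reader might infer that it cannot be made in the ITT set. But plain CT is scheduled for all patients and ASPECTS is read on CT, so the plain CT results may well include ASPECTS. Only the perfusion part is partial, and the SAP says as much. What remains is that the SAP does not state which reading it means.
- **ASPECTS is neither unused nor excluded.** It is summarised by arm, with change from baseline. The covariate list is worded as examples, so ASPECTS is unnamed rather than ruled out. The regression itself is conditional.
- **No bias arises.** A reader might infer that leaving ASPECTS out distorts the treatment comparison. Under randomization it does not, and chance imbalance is reflected in the confidence interval.
- **One covariate set for all outcomes is a defensible choice.** No power target is set for infarct volume, so no stated design property is missed.
- **Some arguments lie outside the document.** The SAP does not say why some patients would have perfusion CT, or what perfusion CT measures relative to a later plain CT. The point does not rely on either.

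After these allowances, two things remain: the comparison has no stated quantity or method, and a relevant baseline reading already planned is not named in the model.

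**Conclusion.** The point holds in a limited form. The SAP announces a comparison of day 5-7 infarct size with baseline CT without specifying the baseline quantity or the method. Its conditional regression for infarct volume does not name baseline ASPECTS, which otherwise has only a descriptive role in the per-protocol set.

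This is a minor improvement to a secondary outcome and not an error in the primary analysis. The benefit is precision alone: a standard error lower by 2.0% to 13.4% for an assumed partial correlation of 0.2 to 0.5. The figure rests wholly on that assumption. Because NIHSS and collaterals are already in the model, the lower end cannot be dismissed.

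**What to change.** In SAP 2.3.2.2, name baseline ASPECTS (core-lab reading, 0-10) as a covariate, alongside the primary-model covariates, in the linear model for infarct volume at 5-7 days in the ITT set, with log transformation if needed. State that this is how baseline infarct extent is accounted for. In 1.3 and 2.1.2.2, word the baseline comparison to match, and keep any comparison with perfusion CT descriptive, in patients who had it, with the number per arm.

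The cost is a sentence or two and one covariate. No new data are needed, since the reading is already planned. The downside is one more covariate with possible missing values, which the regression imputation of baseline data in section 2.4.2 already covers.
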